## 5.2 Procedures for Study Closure

### 5.2.1 Routine study close-out

The study will end when Recovery Force has obtained all data necessary to complete its studies of the test products. Study close-out will follow Recovery Force standard procedures and may include, but is not limited to, review of regulatory documents, collection of completed case report forms, reconciliation of study records, removal or destruction of ancillary study supplies, record retention and final report submission to the IRB.

### 5.2.2 Suspension or premature termination of the study

This study may prematurely terminate at any time because of a regulatory authority decision, a change in opinion of the IRB, or at the discretion of Recovery Force. If the study is temporarily suspended, Recovery Force will provide guidance on timing and procedures for resuming the study. If the study is prematurely discontinued, all study materials must be collected, and all study forms completed to the extent possible.

[figure not shown]
## 6 DATA QUALITY ASSURANCE

Study monitoring is planned at 6 months. The Principal Investigator will be responsible for the accuracy of all study data.

## 7 STATISTICAL METHODS

### 7.1 Determination of Sample Size and Planned Analyses

[name] (University of Massachusetts) is responsible for statistical design and power on this study. First, the team will test the group differences on demographic profiles and between RF1400 (Group 2) and standard-of-care (Group 1). If unbalances on any of these characteristics exist, the Horvitz-Thompson weights or propensity scores will also be adjusted to adjust for bias (d'Agostino, 1998). [name] will also compare the characteristics of the individuals who will drop out of the study with those who complete the study and create weights to adjust for any potential bias. For study, Recovery Force hypothesizes that the in-hospital outcomes measures (minutes of use in the first 24 postoperative hours, number of steps in the first 24 postoperative hours and the amount of

time required by acute care nursing staff to get the patient ready to ambulate) for the patients in RF1400 group (Group 2) will significantly outperform those in standard IPC prophylaxis group (Group 1). Similarly for the Aim 2 at-home outcome measures, (minutes of use per day in the first 14 days of at home use and gait speed at 14 days using the 4-meter walk test, Recovery Force hypothesizes that patients in RF1400 group (Group 2) will significantly outperform those in standard of care group (Group 1). All outcomes are continuously measured. To test Aim 2, let  $E_1$  be the indicator variable of group 1 ( $E_1=1$ ) vs. group 2 ( $E_1=0$ ), and  $Y$  stands for the outcome variable,  $Z$  refers to other relevant background and/or clinical variables (age, gender, comorbidities, etc.), the analysis of covariance (ANCOVA) model will be used to assess the difference between groups, i.e., and the team will have  $Y = \beta_0 + \beta_1 E_1 + \beta_2 Z + \varepsilon$ , estimated to give corresponding  $b$  parameters for  $\beta$  by ordinary regression. The significance of coefficient of  $\beta_1$  will be tested to show the group differences. The interaction term of treatment indicator and center indicators will also be tested to examine the homogenous treatment effect across the two study sites. The study was powered assuming 80% of power and 0.05 significance level; the study will require 130 patients per group to detect a medium effect size (EF) of 0.35 difference between groups for a continuously measured outcome. Assuming up to a 15% dropout, each site will enroll 150 patients in each group. The graph below shows the different sample size requirements to detect a certain EF at power of 0.8 or 0.9.

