11. Group 1 will receive standard of care DVT prophylaxis (which may be compression stockings, standard IPC or no orders) and a daily goal for steps (mobility). Compliance related to DVT prophylaxis will be self-reported by the patient in a journal in terms of total minutes per day. Compliance with mobility goals will be tracked using an activity tracker in addition to being self-reported.

	

12. Group 2 will receive instructions on how many hours per day to use the RF MAC System and a targeted number of steps to achieve per day (from healthcare team). Primary compliance data with DVT prophylaxis will be self-reported in a patient journal. Data related to mobility goals will be collected by the RF MAC System and recorded each day by the patient.

13. A final 4-meter walk test will be administered by the Research Coordinator at the 2-week in-office visit and results will be entered into REDCap.

14. At the end of the study, patients will complete a brief survey regarding their experience with both the standard DVT prophylaxis device and the RF MAC System during their in-home recovery. All participants will receive \$100 as remuneration for their study participation and be asked to sign a compensation receipt form. Participants at Tufts Medical Center will also receive \$21 for parking reimbursement.

15. The home physical therapist will also be asked to complete a brief survey.

--	--

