**At Home:**

Once discharged, patients will continue involvement in the study at home.

Patients in both groups will receive orders for standard of care from their healthcare team. This may or may not include IPC DVT prophylaxis for Group 1. Group 2 will receive orders for use of the RF MAC System. Patients in Group 2 will be sent home with their RF MAC System and a “patient packet” that includes a user manual, charging hub, controllers, additional straps, a list of study contacts, and instructions for returning their devices at the end of the study. Patients in Group 1 will be sent home with the standard of care (as noted in their CRF)

In addition, patients in both Groups 1 and 2 will receive daily at-home mobility goals from their healthcare team (which were noted in the CRF at discharge).

Patients in both groups will receive orders for at-home physical therapy for a minimum of 14 days, which is standard of care for TJR patients discharged to home. The Research Coordinator will record prescribed physical therapy in the patient’s CRF.

Group 1 will receive standard of care DVT prophylaxis (which may be compression stockings, standard IPC or no orders) and a daily mobility goals. Daily mobility goes are expected to prepare patients to complete 2,000 steps a day by the end of the 2-week study period. Compliance will be measured using the activity tracker provided at study enrollment. Patients will be asked to wear the tracker at all times, except during sleep. At the conclusion of the study, the Research Coordinator will record the total activity per day. In addition, the Research Coordinator at each site will call study participants two times during each week of study participation to ensure participants are wearing the activity trackers.

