Group 2 will receive instructions on how many hours per day to use the RF MAC System and a targeted number of steps to achieve per day (from healthcare team). Primary compliance data will be self-reported and collected by the Research Coordinator. Data related to mobility goals will also be collected with the activity tracker. A secondary method of data collection will be the RF MAC System itself. At the end of each day, patients in Group 2 will record the data on the display of the RF MAC System screen, filling in the data for each category in a paper diary provided by the Research Coordinator (provided to Coordinators by Recovery Force). The paper diary will include an image of the screen and users will write the data they see on the screen at the end of each day.

The Research Coordinator will call each participant (in both groups) two times a week during the two-week study. Telephone calls will focus on 1) reminding patients to comply with orders; 2) reminding patients to wear their activity tracker; and 3) reminding patients to comply with DVT prevention orders. The Research Coordinator will answer any questions and confirm the participants are complying with study requirements. The Research Coordinator will also review with the patient the return procedures for the RF MAC, which will involve bringing the device with them to their two-week post-operative office visit.

The patients in both groups will be reminded the day before their 2-week appointment via a telephone call to bring their activity tracker with them to their appointment. The patients in Group 2 will be reminded to also bring back the RF MAC System in its entirety with them to their appointment.

At the 2-week follow up appointment, the Research Coordinator will conduct a final 4-meter walk test. Results will be recorded on the patient's CRF in REDCap.

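### At-home minutes of use per day compares two care packages and cannot be read as compliance, because what is ordered differs by group

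*Combined protocol and SAP*

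**What the plan says.** **The test.** Section 7.1 lists "minutes of use per day in the first 14 days of at home use" among the at-home outcomes. Its hypothesis is that "patients in RF1400 group (Group 2) will significantly outperform those in standard of care group (Group 1"). The model is an ANCOVA on the outcome itself, with no denominator. The covariates given as examples are background and clinical variables; the at-home order is not among them.

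**The label.** Synopsis, At Home, step 11, on Group 1: "Compliance related to DVT prophylaxis will be self-reported by the patient in a journal in terms of total minutes per day". Step 12, on Group 2: "Primary compliance data with DVT prophylaxis will be self-reported in a patient journal". Section 2.4, At Home, repeats for Group 2: "Primary compliance data will be self-reported and collected by the Research Coordinator".

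**The orders.** Section 2.4, At Home: "Group 2 will receive instructions on how many hours per day to use the RF MAC System", and all of them take the system home. For the controls, Synopsis step 11 says: "Group 1 will receive standard of care DVT prophylaxis (which may be compression stockings, standard IPC or no orders"). Section 2.4 says of the standard-of-care orders: "This may or may not include IPC DVT prophylaxis for Group 1".

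**What is recorded.** The at-home order is entered in the CRF before discharge (Synopsis step 9; section 2.4, end of In-Patient). No analysis use of it is stated.

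**The concern.** Compliance is use relative to what was asked for. A control with no order cannot be non-compliant, yet may contribute zero minutes. A control ordered fewer minutes than Group 2 can follow the order fully and still report less use. Raw minutes therefore mix two things: what was ordered, which differs by group by design, and how well patients followed it.

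The plan calls minutes per day compliance and then tests minutes per day between groups. Followed as written, it could lead to a report that the device improves compliance at home when the orders alone produced the difference. Three scoring questions are also left open, and each can move the result: whether a control without an order counts as zero, missing or not applicable; whether stocking time counts as use; and whether minutes are ever related to ordered minutes.

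**Working it through.** **Plan's own figure.** For effect size 0.35, 80% power and two-sided 0.05, n = 2(1.960 + 0.842)²/0.35² = 128.1, so 129 per group. The t-test version gives 129.1, so 130. The stated 130 reproduces and is not in question; it is used below as the number analysed per group.

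**Inputs.** From the documents: 130 per group and 0.05. Assumed, because the documents give no value: equal adherence in both groups; *c*, the coefficient of variation of daily minutes, at 0.25, 0.5 and 0.8; *q*, the share of Group 1 contributing zero minutes for lack of a counted order (no order, or stockings if stocking time is not counted); *r*, minutes ordered for the rest of Group 1 relative to Group 2.

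**Formulas.** Scale Group 2 to mean 1 and variance c². Then:

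- Mean1 = (1 − q)r
- Var1 = (1 − q)r²(1 + c²) − Mean1²
- z = (1 − Mean1)/√[(Var1 + c²)/130]
- P(Group 2 wins) = Φ(z − 1.96); P(Group 1 wins) = Φ(−z − 1.96)

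With identical orders (q = 0, r = 1), z = 0 and each side wins 2.5% of the time.

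**Equal ordered minutes (r = 1), q = 0.10.**

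- c = 0.8: Var1 = 0.9 × 1.64 − 0.81 = 0.666; z = 0.1/√(1.306/130) = 0.998; Φ(−0.962) = 0.168.
- c = 0.25: Var1 = 0.9 × 1.0625 − 0.81 = 0.146; z = 0.1/√(0.209/130) = 2.495; Φ(0.535) = 0.704.

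**Equal ordered minutes (r = 1), q = 0.20.**

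- c = 0.8: Var1 = 0.8 × 1.64 − 0.64 = 0.672; z = 0.2/√(1.312/130) = 1.991; Φ(0.031) = 0.512.
- c = 0.25: Var1 = 0.8 × 1.0625 − 0.64 = 0.210; z = 0.2/√(0.2725/130) = 4.368; Φ(2.408) = 0.992.

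| Share of Group 1 at zero | c = 0.8 | c = 0.5 | c = 0.25 |
|---|---|---|---|
| 10% | 0.168 | 0.329 | 0.704 |
| 20% | 0.512 | 0.831 | 0.992 |

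(Probability that Group 2 wins although adherence is equal.)

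**Unequal ordered minutes, nobody at zero (q = 0).** At r = 0.8 Group 2 wins with probability 0.605, 0.945 and 1.000 (c = 0.8, 0.5, 0.25). At r = 1.2 Group 1 wins with probability 0.446, 0.831 and 1.000. The distortion can go either way.

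**Cross-check with another model.** Beta-distributed adherence fractions, 4,000 simulated trials per cell, unadjusted t-test. With mean 0.5 and SD 0.25 (c = 0.5), Group 2 wins in 33% of trials at a 10% zero share and 82% at 20%, against 0.329 and 0.831 above. With mean 0.7 and SD 0.2, the figures are 63% and 98%.

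**The case against.** The strongest reply is that section 7.1 claims no more than it tests. It says Group 2 will have more minutes, and it calls the at-home comparator the standard of care group where the in-hospital one is the standard IPC prophylaxis group. Read with the statement of what standard care may be, that already suggests a comparison of care packages. This stands in part: the randomised contrast is valid, and a Group 2 win would be a real difference in minutes. It does not remove the difficulty that the Synopsis calls those same minutes compliance.

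A reader might infer more than the documents support:

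- **That an at-home adherence claim is promised.** None is stated. At-home minutes are in none of Hypotheses 1 to 4 and not in the secondary objectives; as an outcome they appear only in section 7.1.
- **That at-home compliance is a primary endpoint.** In section 2.4 the words on primary compliance data are followed by a secondary method of collection, the device display. Primary there ranks data sources.
- **That Hypothesis 1 extends to the home.** Section 2.2 omits the in-hospital limit that the Synopsis gives, but keeps the fully operational device and the standard IPC comparator, which fit the in-patient setting. The mismatch is editorial.

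It is also fair to say that the illustration is unadjusted while the plan uses ANCOVA. Baseline covariates can reduce residual variance, but they do not remove a mean difference created by orders. Adding the order as a covariate is not a clean remedy, because it is set after randomisation and largely determined by group.

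**Conclusion.** The point holds and is moderate. The at-home minutes contrast is a sound randomised comparison of total prophylaxis time under two care packages. It is not a measure of compliance, because the orders differ by group and can alone produce, enlarge, cancel or reverse a difference.

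The size in this trial is unknown. The 17% to 70% (10% of Group 1 at zero) and 51% to 99% (20%) rest on assumed equal adherence, equal ordered minutes and a coefficient of variation of 0.8 to 0.25. They show the mechanism and should not be quoted as this trial's false-positive rate. As a test of total minutes, those wins would not be errors; they mislead only if reported as compliance.

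**What to change.** In section 7.1, define the at-home outcome along these lines: reported minutes of prophylaxis per day over the first 14 days at home, compared by randomised group, using the minutes actually reported regardless of the order. Score zero only when zero use is reported, and missing when there is no report. State before any data are seen whether stocking minutes count. Add that the analysis compares total prophylaxis time under two care packages and does not test compliance.

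Report adherence separately, as minutes used divided by minutes ordered, only for patients whose recorded order has a duration. Present it by order type, as descriptive and non-randomised, with no-order patients shown as not applicable. It may not be computable for some of Group 1, since the documents do not say that Group 1 orders carry a duration.

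Two checks go with this. Confirm that the CRF holds order type and any ordered duration as separate fields. Confirm that Group 1 receives a journal: Synopsis step 11 relies on one, but the Synopsis lists it only in the Group 2 packet, and section 2.4, Study Preparation, describes it for steps and RF MAC use. Without it, zero use in Group 1 cannot be told from missing data. As an editorial matter, give Hypothesis 1 in section 2.2 the same in-hospital limit as the Synopsis.

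The cost is a few sentences of SAP text, one hypothesis sentence, and possibly a CRF field and a Group 1 journal. The downside is that the sponsor gives up an at-home compliance claim from raw minutes.

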Methodology Overview	
Once IRB approval has been obtained, the sponsor team, [name] (University of Massachusetts) and Dr. [name] will begin training Research Coordinators at two study sites: Tufts Medical Center and Eskenazi Hospital. Research Coordinators will establish data collection methods (Case Report Forms) in REDCap (an online database for research data and surveys) at each site, RF MAC Systems will be shipped to the sites, charged and prepared for assignment to patients as they are enrolled in the study at their final pre-operative appointment. Each site will enroll 150 patients (300 patients total) and patients will be randomized in to one of two groups: Control (Group 1) or Intervention (Group 2). Participants will receive an identification number and all data collected will be password-protected. The study consists of two parts: in-patient and at-home. All participants will participate in both parts of the study.
 
In-Patient:
 
 
1. In the pre-operative appointment, the Research Coordinator will enroll participants and they will be randomly assigned to a study Group (control or intervention) and baseline information will be collected on the CRF.
 
2. A 4-meter walk test will be performed and the Research Coordinator will enter results in the patients CRF.
 
3. On the day of surgery, the patient will receive standard of care for each site for patients undergoing a THR or TKA. Patients in the control group (Group 1) will receive the site's standard of care IPC for DVT prophylaxis. Group 2 (intervention) will receive the RF MAC System for DVT prophylaxis. In addition, patients in both groups will receive an activity tracker.
 
4. In the first 24 hours post-operative, the Research Coordinator will visit the patient's room for observation a total of two times. During these visits, the Research Coordinator will visually observe the status of the DVT prevention device (control or intervention) to determine if it is properly applied to the patient's lower extremities and fully operational. This information will be recorded in REDCap. For Group 1 (control), this information will be collected by via observation by the Research Coordinator and patient interview. For the MAC System Group 2, this information will be collected automatically by the device and recorded by the Research Coordinator during the periodic visits.
 

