### **2.2 Primary**

Conduct a randomized comparative study of DVT prophylaxis using either standard IPC (Group 1) or the RF MAC system (Group 2) in 300 patients after TJR surgery.

Hypothesis 1: Study participants who use the RF MAC will have rates of adherence to wear time of a fully operational device that are at least 25% higher than those using standard IPC devices.

Hypothesis 2: Patients wearing the RF MAC in the first 24 hours following surgery will take at least 25% more steps as measured by an activity tracker than those patients using standard of care IPC devices.

Hypothesis 3: Patients who use the RF MAC will have a mean gait speed at 14 postoperative days that is at least 20% higher than patients receiving standard of care as measured by the 4-meter walk test.

Hypothesis 4: The time required for preparing patients to ambulate will be 50% less using the RF MAC than standard IPC devices.

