**In-Patient:**

In the pre-operative appointment, the Research Coordinator will enroll participants and they will be randomly assigned to a study group (control or intervention). Patients will be assigned a participant number and that number will be recorded on their Informed Consent and the CRF. Only the Research Coordinators at each site and the PI will have access to the key that connects participant numbers to patient names.

A baseline 4-meter walk test will be performed and the Research Coordinator will enter results in the patients CRF. The protocol for the 4-meter walk test is described in the site protocols found in Appendix A (Tufts Medical Center) and Appendix B (Eskenazi Hospital).

On the day of surgery, the patient will receive standard of care for each site for patients undergoing a THR or TKA. Patients in the control group (Group 1) will receive the site's standard of care IPC for DVT prophylaxis. Group 2 (intervention) will receive the RF MAC System for DVT prophylaxis. In addition, patients in both groups will receive an activity tracker and corresponding waterproof pouch to hold the activity tracker. The display screen of the activity tracker will be covered with tape during the study period. Tape will be removed by Research Coordinators and data will be collected from the device at the end of the study period.

Research Coordinators will be responsible for providing device training to participants prior to discharge. This will be conducted using verbal explanation, demonstration and return demonstration. It is expected to require 10-15 minutes to complete training on the RF MAC System and review all required study materials, the use of the activity tracker and follow-up requirements.

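### The ANCOVA for day-14 gait speed (Hypothesis 3) does not name pre-operative 4-meter walk speed as a covariate, although it is collected on every patient and could narrow the interval at no cost

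*Combined protocol and SAP*

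**What the plan says.** Hypothesis 3 (section 2.2 and Synopsis) is that RF MAC patients "will have a mean gait speed at 14 postoperative days that is at least 20% higher than patients receiving standard of care", measured by the 4-meter walk test.

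Section 7.1 lists day-14 gait speed among the Aim 2 at-home outcomes. For Aim 2 it gives a regression of the outcome on a group indicator and on Z, fitted by ordinary regression, and tests the group coefficient. Z "refers to other relevant background and/or clinical variables (age, gender, comorbidities, etc". Site enters only through a homogeneity check: "The interaction term of treatment indicator and center indicators will also be tested".

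The same walk test is done before surgery. Section 2.4, In-Patient, says "A baseline 4-meter walk test will be performed and the Research Coordinator will enter results in the patients CRF", and step 2 of the In-Patient list in the Synopsis agrees: "A 4-meter walk test will be performed and the Research Coordinator will enter results in the patients CRF". No section gives this measurement a role in the analysis.

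On size, section 7.1 says "the study will require 130 patients per group to detect a medium effect size (EF) of 0.35 difference between groups", at 80% power and a 0.05 level, with up to 15% dropout.

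**The concern.** A pre-treatment measurement of the outcome itself is usually the first covariate to put into an ANCOVA, because it often explains more outcome variance than demographic variables do. Here the model names age, gender and comorbidities and leaves the rest to a later decision. Two models for Hypothesis 3 are therefore both consistent with the text, one with baseline walk speed and one without.

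What is at stake is precision on one of the four hypotheses listed as primary. If baseline speed is left out, the estimate remains valid, but its confidence interval is wider than it need be given data the trial will already hold.

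**Working it through.** **1. The plan's own figure.** For a two-sample t-test, two-sided 0.05, standardised difference d = 0.35 and 80% power, the required size is 129.1, rounded up to 130 per group. Power at 130 per group is 80.3%. The stated 130 reproduces as a comparison with no covariates.

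**2. Inputs.**
- Completers per group: 75 per group at each of two sites (Table 1 in section 2.4; section 2.5) gives 150, and 150 × 0.85 = 127.5. Unadjusted power at d = 0.35 is then 79.5%.
- Correlation ρ between pre-operative and day-14 speed: not in the documents; assumed 0.3, 0.5 and 0.7.
- Share of outcome variance explained by the named covariates, R²z: not in the documents; assumed 0.10 or 0.20.
- Share of baseline-speed variance explained by the same covariates, q: not in the documents; assumed 0.10 or 0.20. Z is treated as one score that predicts both speeds in the same direction.
- Mean and SD of gait speed: not in the documents, so the coefficient of variation (CV) is assumed at 50%, 40% and 30%.

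**3. Formulas.** With Z and baseline speed both in the model,

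R² = (R²z + ρ² − 2·√R²z·ρ·√q) / (1 − q).

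The interval width relative to Z alone is √[(1 − R²)/(1 − R²z)]. Power uses the noncentral t with d divided by √(1 − R²z) for Z alone, or by √(1 − R²) with baseline speed added. The test is of a zero group coefficient, as in section 7.1.

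**4. One case in full.** Take ρ = 0.5, R²z = 0.10, q = 0.10.
- R² = (0.10 + 0.25 − 0.10)/0.90 = 0.278.
- Width ratio = √(0.722/0.90) = 0.896, so the interval narrows by 10.4%.
- Effective d is 0.35/√0.90 = 0.369 with Z alone (power 83.5%) and 0.35/√0.722 = 0.412 with baseline added (power 90.6%). The gain is 7.1 points.

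**5. Full range beyond Z** (over the four combinations of R²z and q; gains taken before rounding):

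| Assumed ρ | Interval narrows by | Power gain at d = 0.35 (points) |
|---|---|---|
| 0.3 | 0.8-2.5% | 0.5-1.8 |
| 0.5 | 7.3-10.4% | 4.3-7.1 |
| 0.7 | 21.9-25.5% | 10.3-14.1 |

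If Z explained nothing, the narrowing would be 1 − √(1 − ρ²) = 4.6%, 13.4% and 28.6%. The table is the fairer comparison, since the plan already adjusts for Z.

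**6. At the difference in Hypothesis 3.** A 20% difference in means gives d = 0.20/CV.

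| CV | d | Unadjusted power | Gain beyond Z at ρ = 0.3 / 0.5 / 0.7 (points) |
|---|---|---|---|
| 50% | 0.40 | 88.9% | 0.3-1.2 / 2.5-4.4 / 5.0-7.6 |
| 40% | 0.50 | 97.8% | 0.1-0.3 / 0.4-1.0 / 0.6-1.3 |
| 30% | 0.667 | near 100% | about 0 |

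The plan's d = 0.35 corresponds to a 20% difference only if the CV is 0.20/0.35 = 57%. The proportional narrowing of the interval in step 5 does not depend on the CV.

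**7. The other enrolment reading.** The dropout sentence in section 7.1 puts 150 patients in each group at each site, which conflicts with 75 per group per site elsewhere. On that reading there would be 300 × 0.85 = 255 completers per group, unadjusted power at d = 0.35 would be 97.6%, and the gain beyond Z at most 1.4 points. The width ratio does not contain the sample size, so the narrowing would be unchanged.

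**The case against.** The strongest reply is that the open list already allows baseline speed, so a sensible analyst would include it. That is right as far as it goes: a reader might infer that the plan excludes the covariate, and the text does not say so. What remains is that nothing requires it.

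A second reply is that the gain may be small. This also stands in part. Every precision figure rests on assumed values. At correlation 0.3 the interval narrows by at most 2.5% beyond Z, and if the CV is 40% or less, power at a 20% difference is already so high that little can be added. The case then rests on the width of the interval, not on power.

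Four stronger readings are tempting and are not supported:
- **Inflated type I error.** In simulation with no effect, each single pre-chosen model rejected in about 5% of trials. Taking the smallest p-value of four covariate sets gave 8.9-12.1%, but nothing in the plan proposes that. It is a worst case, not a property of the planned test.
- **An unstable conclusion.** At d = 0.35 the significance verdicts of the two models differed in 4.6%, 10.0% and 15.8% of simulated trials at correlations 0.3, 0.5 and 0.7. Most of these are trials that reach significance only with baseline speed included, so they largely restate the power gain.
- **Distortion by weighting.** Section 7.1 also says "If unbalances on any of these characteristics exist, the Horvitz-Thompson weights or propensity scores will also be adjusted to adjust for bias", with no threshold and no rule for choosing between the two. That sentence covers all outcomes and words seem to be missing just before it. The two options can overlap, because such weights are commonly built from propensity scores. Weights built on the same Z, applied in every simulated trial, moved the estimate by a median of 0.001 SD. That does not test the conditional rule itself, but no effect on the result has been shown.
- **A wrong sample size.** The 130 per group reproduces without any covariate.

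**Conclusion.** The point holds as one of precision and pre-specification, and the change should be made. The Hypothesis 3 model leaves out by name the one covariate that is the outcome's own baseline. The gain ranges from slight to about a quarter of the interval width, depending on a correlation that the documents do not give. A power gain of practical size needs a correlation of about 0.5 or more together with a standardised difference nearer 0.35-0.40 than 0.50. Confidence is medium: the textual gap is certain and its size is assumed.

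**What to change.** Before outcome data are seen by group, state in section 7.1 that the ANCOVA for day-14 gait speed includes pre-operative 4-meter gait speed as a covariate alongside age, gender and comorbidities. Name the comorbidity variable and delete the open ending so that the list is closed.

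Optionally, make the imbalance-triggered weighting a sensitivity analysis with one named method. This is tidier pre-specification with no shown effect on the result. The separate dropout step ("create weights to adjust for any potential bias") and the site-interaction test need not change for this point.

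While section 7.1 is open, reconcile its enrolment per group and site with Table 1 and section 2.5.

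The cost is wording only: no new data, visits or patients.
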